## Recruitment

1 \* Describe plans for recruitment, including the identification of potential participants (or acquisition of charts/records/samples) and initial interactions with them: (If this study involves the VA please list all sites at which recruitment will take place.):  
main study and sub study:

Potential participants will be referred by their treatment team or through self-referral via IRB approved flyers that will be posted in the waiting room at the clinic sites. Potential participants will be screened in the clinic on a scheduled screening visit day. During screening, the RA will briefly describe the study protocol, including potential risks and benefits and obtain written consent for completion of the screening questions. Potential participants who do not meet all inclusion criteria or meet any of the exclusion criteria will not be eligible for the study.

We will also obtain a list of current clinic participants so that we can screen the clinic for eligible participants. All eligible individuals will be reviewed with the clinic staff to ensure they are stable enough to approach for the study.

2 \* Describe measures that will be implemented to avoid participant coercion or undue influence (if not applicable to the study, enter "N/A"):

Participants will be reminded at every visit that their participation is completely voluntary and neither their care will not be affected by their willingness to participate or not.

3 \* Who will recruit participants (or acquire charts/records/samples) for this study? (Check all that apply)

PI  
 Study Staff  
 Third Party

3.1 If you are using a third party, specify Third Party Recruiters:

4 Upload any recruitment tools such as screening/telephone scripts and introductory letters (do not upload advertisements here):

| Name | Created | Modified Date |
|------|---------|---------------|
|------|---------|---------------|

There are no items to display

## Advertising

1 \* Will you be using advertisements to recruit potential participants?

Yes  No

ID: V1EW4E0BCCF811000  
Name: v2\_Advertising

## Advertising Detail

You indicated that you will be using advertisements to recruit potential participants.

1.1 \* Select the mode(s) of advertising (check all that apply):

- Radio
- Internet
- Print
- Television
- Other

1.1.1 If Other, specify:

1.2 \* Provide exact text of all proposed advertisement(s):

Do you want to quit smoking? Are you willing to join a research study?

University of Maryland Baltimore is looking for 300 volunteers to participate in a research study on various smoking cessation treatments.

You qualify for the study if you are: HIV positive, age 18 and above, smoked at least one cigarette in the last week. willing to quite smoking, if a woman, should not be pregnant or be a nursing mother.

Qualified participants will receive: study related counseling on how to quit smoking, study related medicines, compensation for travel and study related time.

Study length: 36 weeks

Screening and evaluation visits, baseline visit and follow up visit.

Benefits: Participants will receive counseling sessions on how to quit smoking. Receiving medication that can assist with quitting smoking.

Did you know that when you smoke: people with HIV are more likely to develop harmful consequences of smoking than those without HIV. you are more likely to get pneumonia and asthma attacks.

You are more likely to suffer from cancer. You spend money that could be used on other things.

You harm the health of your children and those around you.

The good news is that when you quit: you will be less likely to get pneumonia, asthma and cancer. You will protect your children and those around you.

For more information, please call

University of Maryland Baltimore Smoking cessation study  
on: [name] or [name] or [name]

Or visit the clinic located at the Methadone clinic:

Muthaiga National Teaching and Referral Hospital in Muthaiga, [name].

Sub Study Flyer:

We want to hear your thoughts about HIV, cancer and Alcohol.

Are you willing to join a research study?

University of Maryland Baltimore is looking for volunteers to participate in a research study. You will either complete a one-time interview or participate in a focus group (a group of about 6-8 people responding to several questions in a group room setting).

You qualify for the study if you are: HIV positive, age 18 and above and a smoker

Study length: 1 day

Screening and an interview or screening and a focus group.

## Research Related Risks

**If you uploaded a separate research protocol document in the 'Research Protocol' page, cite the applicable section and page numbers from that document in the answer box below.**

1 \* Individually list each research-related risk, using a separate line for each. Next to each risk, delineate the likelihood/seriousness of the risk, and the provisions for minimizing the risk:

Risks associated with the use of bupropion include allergic reactions (most commonly skin rashes and itching), dry mouth (10%), insomnia (30%), dizziness, tremor, and headaches. Of these, dry mouth and insomnia are most common. These problems are generally well tolerated and transient. The risk of seizure, when using sustained-release bupropion in the dose range used in this study, is 0.1%, a rate similar to that of other antidepressants.

Risks related to participating in research interviews (Research Risk). The risk from research interviews is minimal and relatively uncommon. During assessments participants may be uncomfortable discussing their smoking habits or mental health history and treatments. Participants may become frustrated and tense when they encounter difficulty when completing these measures. Careful planning and observation of the participant's response to these sessions will allow the testing to be completed with a minimum of discomfort. Participants will take breaks when necessary to help alleviate any discomfort. All interviews are trained to recognize signs of distress or anxiety. The participant will be reminded that they can refuse to answer any question that makes them uncomfortable and may take breaks whenever they are needed. There is a slight risk of breach of confidentiality. All data will be coded with an ID number that is unique. All data including information from chart reviews, therapist reports and laboratory results will be label by ID only. Only the study team will have access to the link between the ID and participant's name. Data containing names and personal information will never be included in published materials.

Risks related to participating in Behavioral Treatment for Smoking Cessation (Therapeutic Risk). The behavioral treatment sessions may cause some temporary anxiety or distress due to discussing smoking habits and attempts to quit smoking. The interventionists are all trained mental health providers who will work with the participants to help alleviate any feelings of distress. This risk is minimal and uncommon.

The risks and discomforts for those randomized to receive placebo+standard of care may include nicotine withdrawal symptoms.

Other risks. There are additional types of risks in this study that relate to smoking cessation and its treatment. One is the stress of and symptoms associated with nicotine withdrawal. Depressed mood, insomnia, anger, anxiety, difficulty concentrating, restlessness, and decreased heart rate are all common. However, these symptoms are short-lived and uncomfortable, though well tolerated. There is no evidence in the literature of psychiatric relapse or significant psychiatric worsening in the context of nicotine withdrawal. Further, the use of nicotine replacement products may diminish the withdrawal symptoms.

The risks of experiencing weight gain, appetite change, and irritability are identified as possible long-term risks that are not well tolerated. In the absence of receiving a properly working treatment, you may also experience a possible relapse.

Sub study:

The risk from research interviews is minimal and relatively uncommon. During assessments participants may be uncomfortable discussing their smoking habits, alcohol use, or mental health history and treatments. Participants may become frustrated and tense when they encounter difficulty when completing these measures. Careful planning and observation of the participant's response to these sessions will allow the testing to be completed with a minimum of discomfort. Participants will take breaks when necessary to help alleviate any discomfort. All interviewers are trained to recognize signs of distress or anxiety. The participant will be reminded that they can refuse to answer any question that makes them uncomfortable and may take breaks whenever they are needed.

There is a slight risk of breach of confidentiality. All data will be coded with an ID number that is unique. All data including information from chart reviews, therapist reports and laboratory results will be label by ID only. Only the study team will have access to the link between the ID and participant's name. Data containing names and personal information will never be included in published materials.

## Potential Benefits and Alternatives

**If you uploaded a separate research protocol document in the 'Research Protocol' page, cite the applicable section and page numbers from that document in the answer boxes below.**

1 \* Describe the potential direct benefit(s) to participants:

The great benefit of smoking cessation on lowering risk of mortality, especially cardiac-related mortality, would be especially pronounced in smokers living with HIV/AIDS.

2 \* Describe the importance of the knowledge expected to result from the study:

This study will allow us the opportunity to examine which of the factorial design was the most effective on smoking cessation.

3 \* Describe how the potential risks to participants are reasonable in relationship to the potential benefits:

We believe that the risks to participants in this study are outweighed by the potential societal benefits described above.

4 \* Describe the alternatives to participation in this study. If there are no alternatives, state that participation is voluntary and the alternative is not to participate. For intervention studies, describe appropriate alternative clinical procedures or courses of treatment available to subjects.

There are no alternatives, participation is voluntary and the alternative is not to participate. However, participants who choose not to participate in the study will have the option of receiving bupropion and regular clinical care.

ID: VIEW4E1B5251B0400  
Name: v2\_Potential Benefits and Alternatives

## Withdrawal of Participants

**If the questions below are not applicable to the research (i.e., chart review), enter "N/A".**

1 \* **Describe anticipated circumstances under which subjects will be withdrawn from the research without their agreement:**  
1) They have a serious reaction during the study  
2) They fail to follow instructions from research staff  
3) If the PI decides that the study is no longer in the best interest of the participant.

Withdrawal will take place in the case of a significant side effect or at a participant's request. At discontinuation, interviews and ratings will be performed if possible. If suicidal ideation or intent is observed, the study suicide prevention plan (SPP) will be implemented and the participant will be withdrawn. The SPP consists of immediate psychiatric evaluation, use of a suicide prevention contract, provision of 24-hour access to a physician, referral to emergency services.

2 \* **Describe procedures for orderly termination:**  
The study will conclude after the last participant completes their last assessment interview.

3 \* **Describe procedures that will be followed when subjects withdraw from the research, including partial withdrawal from procedures with continued data collection:**  
When individuals withdraw from the protocol, we will keep all data that was already collected.

ID: VIEW4E1B52531F800  
Name: v2\_Withdrawal of Participants

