5.1 If Yes, what procedures are in place to assure safety?

Screening: If a potential participant scores positive for the suicide screening, he/she will be referred to psychiatric services that are on site at the clinic for further evaluation.

Baseline and other time points: During the baseline interview and all subsequent interview time points (Week 1,2,4,8, 12 and 36), we will be administering a suicide questionnaire (MINI suicide model) as well as a medication side effects check list. If, during the course of a meeting, a participant endorses HI or SI behavior, we will follow our Suicidal or Homicidal Ideation/Intent Checklist (attached in Additional Documents). The document clearly details what to do and who to contact in a situation. [name] is a Physician and will be the first contact in many situations. We are also recruiting at clinic sites, so there will also be several clinicians available on site if needed.

We will also hand out our study business cards at several time points for the study. The card has our contact information on the one side and crisis information and hotline numbers on the second side (attached in Additional Documents).

The CES-D evaluates depressive symptoms but does not assess suicidal ideation or intent. It is important to note that the CES-D is not a diagnostic scale. If a participant has a score of greater than 16 on the CES-D will be referred for further evaluation by a study PI.

ASI-Lite: We will be requesting a certificate of confidentiality.

For All participants: We will provide them with information regarding what to do in case of a psychiatric emergency including contacting a Crisis hotline or going to the closest emergency department for further assessment.

ID: VIEW4E09460F5EC00  
Name: v2\_Surveys/Questionnaires

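### The withdrawal section does not separate stopping study treatment from leaving follow-up, so week-36 outcomes could be lost contrary to the intent-to-treat plan

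*Protocol*

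**What the plan says.** **Withdrawal of Participants, item 1 (protocol).** The form asks when "subjects will be withdrawn from the research without their agreement". The answer lists a serious reaction, "They fail to follow instructions from research staff", and the PI's view that the study no longer serves the participant. Free text then adds: "Withdrawal will take place in the case of a significant side effect", or at the participant's own request. It also has the participant withdrawn if suicidal ideation or intent is seen. The only assessment mentioned is an exit one: "At discontinuation, interviews and ratings will be performed if possible".

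**Item 3 of the same section.** The form asks about procedures on withdrawal, "including partial withdrawal from procedures with continued data collection". The whole answer is: "When individuals withdraw from the protocol, we will keep all data that was already collected".

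**Elsewhere.**
- Protocol, Study Procedures (Follow Up Assessment Interviews): all participants are re-assessed at about weeks 12 and 36.
- Protocol, Overview of Analytic Methods: the primary analyses are intent-to-treat.
- SAP, Missing Data: the team will try to assess all participants at follow-up whether or not they engage with cessation services, and to bring back for week 36 those who miss interim visits. Someone who refuses contact or is otherwise lost to contact is counted as non-abstinent.
- Protocol, Surveys/Questionnaires, item 5.1: "we will be administering a suicide questionnaire (MINI suicide model) as well as a medication side effects check list". This is planned for baseline and for every later visit, that is, weeks 1, 2, 4, 8, 12 and 36.

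**The concern.** The form's wording is withdrawal from the research, not from study medication, and it asks directly about continued data collection. The answer leaves that part open. Two staff members could treat the same participant differently, one ending all contact and the other inviting the person to week 36, and each could point to the protocol in support.

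Some of the grounds could depend on treatment. Side effects may be more frequent on bupropion than on placebo, and not following instructions is a post-randomisation behaviour that intent-to-treat follow-up is meant to keep in the analysis. If such people are not assessed at week 36 and are scored as smoking, those who did quit are miscounted. If more of them are on bupropion, the drug effect is understated. A primary outcome that was never collected cannot be recovered at analysis.

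**Working it through.** **1. The passages side by side.** The follow-up statements in Study Procedures and in the SAP cover all participants and make no exception for people whom staff withdraw. Withdrawal of Participants provides for an exit rating and for keeping existing data, and does not mention week 36. The SAP's re-engagement sentence is about missed interim visits. Its non-abstinent rule is about refusal or loss of contact. None of these names a reachable person whom staff have removed.

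**2. Can the exit rating stand in for week 36?** The post-baseline safety checks before the endpoint are at weeks 1, 2, 4, 8 and 12. A rating at one of those visits falls between 36 − 12 = 24 and 36 − 1 = 35 weeks before the primary endpoint, so it cannot replace it.

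**3. The plan's own figures.** 300 × 0.80 / 4 = 60 per cell, and 300 × 0.80 / 2 = 120 per main-effect condition. Power for two proportions (normal approximation, pooled variance under the null, two-sided alpha 0.05) is 86.9% for 10% vs 25%, and 84.3% for 7% vs 20%. The claim of more than 80% reproduces.

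**4. Direction and rough size.** The documents give no withdrawal rate, so the shares w below are assumptions. Inputs: drug comparison, 10% vs 25% (Sample Size and Data Analysis), 300 / 2 = 150 randomised per condition, no other losses, and withdrawn people scored as smoking.

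If withdrawn people would have quit at their own condition's rate, the observed rate is the true rate × (1 − w).

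| w placebo / bupropion | Observed rates | Difference (points) | Odds ratio | Power |
|---|---|---|---|---|
| 0% / 0% | 10.0% vs 25.0% | 15.0 | 3.00 | 93.2% |
| 5% / 5% | 9.5% vs 23.75% | 14.25 | 2.97 | 91.6% |
| 10% / 10% | 9.0% vs 22.5% | 13.5 | 2.94 | 89.8% |
| 5% / 10% | 9.5% vs 22.5% | 13.0 | 2.77 | 87.1% |
| 0% / 10% | 10.0% vs 22.5% | 12.5 | 2.61 | 83.9% |

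Equal withdrawal leaves the risk ratio at 2.5, because (1 − w) cancels. Unequal withdrawal does more.

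**5. A less generous assumption.** People taken off bupropion may not quit at 25%. Suppose that in the 0% / 10% case they quit at the placebo rate of 10%:
- followed to week 36: 0.90 × 25% + 0.10 × 10% = 23.5%, a difference of 13.5 points, odds ratio 2.76, power 88.3%;
- scored as smoking: 0.90 × 25% = 22.5%, a difference of 12.5 points, odds ratio 2.61, power 83.9%.

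The scoring then costs 13.5 − 12.5 = 1.0 point, against 15.0 − 12.5 = 2.5 points in the last row of the table. The other 1.5 points come from the lower quit rate assumed after stopping the drug, which follow-up would not restore. If everyone withdrawn truly smokes, the scoring costs nothing.

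**The case against.** The strongest reply is that the default is already in the plan. The follow-up statements cover everyone without exception, the analysis is intent-to-treat, and the withdrawal section does not forbid a week-36 visit. The SAP's non-abstinent rule probably reaches these people as lost to contact, and the SAP allows a sensitivity analysis with multiple imputation if needed. Item 3 reads most naturally as being about participants who choose to leave, for whom keeping existing data is ordinary practice. Files not shown could settle the matter: the study schedule, consent form and suicide/homicide checklist under Additional Documents, and the research plan under DHHS Funded Study.

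Much of this stands. It narrows the point to an ambiguity with a partial safeguard. It does not close it: item 1 concerns people removed without their agreement, item 3 is the only statement on what happens to data afterwards, and no available text says that these people stay in follow-up. Scoring a missing outcome is also no substitute for collecting one that could have been had.

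A reader might infer that the protocol bars week-36 assessment after staff withdrawal, or that the trial is underpowered as a result. Neither is supported. The section is silent rather than prohibitive, and every scenario above stays over 80% power. Dosage adjustment is also allowed to control adverse effects (Medication Intervention), and the commonest side effects are described as generally well tolerated (Research Related Risks), so withdrawals may be few.

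**Conclusion.** The point holds as a needed reconciliation. Followed literally, the withdrawal section can take reachable, randomised participants out before the primary endpoint for reasons that may differ by arm, which does not fit the follow-up and intent-to-treat statements elsewhere.

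The size is unknown and probably small. Under an assumed 0% placebo / 10% bupropion withdrawal, scoring these people as smoking costs about 1.0 to 2.5 points of the 15-point difference, depending on whether they would have quit at 10% or at 25%. With more withdrawal on bupropion, the direction is towards no drug effect. These figures rest on assumed rates and no other losses. Confidence is medium, because an attachment may already cover the matter. The change is worth making because it is simple and protects the primary outcome.

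**What to change.** Reconcile Withdrawal of Participants with Follow Up Assessment Interviews, Overview of Analytic Methods and the SAP's Missing Data section by separating stopping study treatment from leaving follow-up.

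- **Protocol:** state that a participant taken off medication or PSF stays in follow-up for the week-12 and week-36 smoking-status and expired-CO assessments, and is analysed as randomised with the observed outcome. The exceptions are a participant who withdraws consent for follow-up, or a responsible clinician who judges contact inappropriate. If an attachment already says this, a cross-reference is enough.
- **SAP:** add one clause that a staff-withdrawn participant with no week-36 outcome falls under the existing non-abstinent rule, with numbers reported by arm and reason. Follow-up will reduce missing outcomes but not abolish them, so the clause is needed either way.

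The clinical grounds for withdrawal stay with the sponsor.

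**Cost:** up to two visits per withdrawn participant, both already in the schedule and paid at $5 each (2 × $5 = $10), plus staff time. A protocol modification is needed, and possibly updated English and Swahili consent forms, which are stamped in Nairobi. Around 200 people had been consented when the protocol's sample-size note was written, so outcomes of anyone already withdrawn may not be recoverable.

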## Privacy of Participants

**If the study does not involve interaction with participants, answer "N/A" to the questions below.**

- 1 \* Describe how you will ensure the privacy of potential participants throughout the study (**privacy refers to persons and their interest in controlling access to themselves**):  
All in person research assessments and focus groups will be conducted in private rooms
- 2 \* Describe the location where potential participants will receive research information and detail the specific actions the study team will take to ensure adequate privacy areas:  
Potential participants will receive research information in a private room for in person interviews.
- 3 \* Describe potential environmental stressors that may be associated with the research:  
We are not aware of any potential environmental stressors that may be associated with the research.
- 4 \* Will this study have a site based in the European Union?  
 Yes  No
- 5 \* Will the study have planned recruitment or data collection from participants while they are located in the European Union?  
 Yes  No

Access link below for information about the EU General Data Protection Regulations to assist in answering these questions.

<https://www.umaryland.edu/oac/general-data-protection-regulation/>

